4.0 Treatment Assignment/Randomization

The following measures will be taken to ensure double-blinded randomization. Prior to the initiation of the study, computer-generated tables will be created in Excel to assign each patient a randomization number. This master list will be kept with a statistician and research coordinators, who do not have any patient contact. Based on his/her corresponding generated number (even or odd), the patient will be assigned to his/her therapeutic arm (methylprednisolone and ketorolac, respectively). The statistician will use an equally weighted random number generator to create these assignments. Therefore subjects will have an equal chance of being assigned to either treatment arm. Separate lists for male and female participants will also be generated to ensure equal gender participation. The statistician will then prepare an opaque envelope for each subject number. The unique subject number will be written on the visible outside surface of each envelope. The corresponding treatment arm assignment will be inside the envelope. The statistician will seal each envelope individually and send all of the envelopes to the research coordinator ([name]) prior to patient enrollment. The sealed opaque envelopes will be divided equally among the clinics and kept in locked containers in the research coordinator's office. The study staff will not have access to the envelopes. After ensuring that the patient has completed the ASES questionnaire (to establish a baseline prior to the injection), the study staff will contact [name] or [name] to provide them with the patient's first and last names as well as the MRN. The research coordinator will open one of the sequentially numbered envelopes to assign each patient the corresponding subject number (written on the outside of the envelope), and a member of the clinic staff will prepare the appropriate injection (see below) for the assigned treatment arm. The syringe will be covered with opaque tape prior to being given to the surgeon for administration. The injection will take place in a private clinic room in compliance with the Health Insurance Portability and Accountability Act (HIPAA) guidelines. The blinded surgeon will administer the injection into the subacromial space using standard bony landmarks from the posterolateral approach. The clinic staff will file the drug accountability log after preparing the injection and they will not disclose the treatment arm assignment to the patient nor the provider. This will maintain the blinding for both the patient and research surgeons. Patients' subject number will be recorded on their consent form and in their electronic medical record. Envelopes will be destroyed at the end of the study by the research coordinators. The statistician will unlock the master list only after patient enrollment and follow-up are complete, or if mandated by any regulatory body. Blinding will also be uncovered in case of a patient developing an adverse event while being followed in the trial.

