7.0 Adverse Events or Unanticipated Problems involving Risk to Participants or Others

Most of these contra-indications are retrieved from the medications package inserts. Due to the randomization and blinding design of the study, a contra-indication to either drug (methylprednisolone acetate or ketorolac tromethamine) is considered an absolute contra-indication for the patient to be enrolled in the study. Subjects meeting any of these conditions at baseline will be excluded from study participation. These conditions include: allergy/intolerance to steroids or NSAIDs symptoms less than one month, pregnancy or breastfeeding, pre-existing asthma, psychiatric illness, previous shoulder injection within the past three months, evidence of other confounding shoulder pathology on plain radiographs such as calcific tendonitis, MRI evidence or history of rotator cuff tear, active comorbidities of the ipsilateral extremity such as lateral epicondylitis and cervical radiculopathy, moderate to severe glenohumeral arthritis, systemic inflammatory conditions, kidney or liver disease, gastrointestinal (GI) ulcers, bleeding disorders, pending litigation or work-related claims related to the shoulder, previous shoulder surgery on the

affected shoulder, evidence of local infection, evidence of adhesive capsulitis, evidence of shoulder instability, and bilateral shoulder pain.

The International Council for Harmonisation of Technical Requirements for Pharmaceuticals for Human Use (ICH) defines an adverse event (AE) as any untoward medical occurrence in a patient or clinical investigation subject administered a pharmaceutical product regardless of its causal relationship to the study treatment. An AE can therefore be any unfavorable and unintended sign, symptom, or disease temporally associated with the use of medicinal product. The occurrence of an AE may come to the attention of study personnel during study visits and interviews of a study recipient presenting for medical care, or upon review by a study monitor.

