All AEs including local and systemic reactions not meeting the criteria for “serious adverse events” should be captured on the appropriate case report form. Information to be collected includes event description, time of onset, clinician’s assessment of severity, relationship to study product (assessed only by those with the training and authority to make a diagnosis, which would include MD, PA, Nurse Practitioner, DO, or DDS), and time of resolution/stabilization of the event. All AEs occurring while on study must be documented appropriately regardless of relationship. All AEs will be followed to adequate resolution.

Any medical condition that is present at the time that the patient is screened should be considered as baseline and not reported as an AE. However, if it deteriorates at any time during the study, it should be recorded as an AE.

All AEs must be graded for severity and relationship to study product. In such cases, the statistician will uncovering the patient blinding and randomization process to reveal the medication that was administered to the patient.

Severity of Event

All AEs will be assessed by the clinician using a protocol defined grading system. For events not included in the protocol defined grading system, than the following guidelines will be used to quantify intensity.

Mild – Events require minimal or no treatment and do not interfere with the patient’s daily activities; **Moderate** – Events result in a low level of inconvenience or concern with the therapeutic measures; **Moderate** – Events may cause some interference with functioning; **Severe** – Events interrupt a patient’s usual daily activity and may require systemic drug therapy or other treatment. Severe events are usually incapacitating; and **Life threatening** – Any adverse drug experience that places the patient or subject, in the view of the investigator, at immediate risk of death from the reaction as it occurred, i.e., it does not include a reaction that had it occurred in a more severe form, might have caused death.

Changes in the severity of an AE should be documented to allow an assessment of the duration of the event at each level of intensity to be performed. Adverse events characterized as intermittent require documentation of onset and duration of each episode.

Relationship to Study Products

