The clinician's assessment of an AE's relationship to test article is part of the documentation process, but it is not a factor in determining what is or is not reported in the study. If there is any doubt as to whether a clinical observation is an AE, the event should be reported. All AEs must have their relationship to study product assessed using the terms: associated or not associated. In a clinical trial, the study product must always be suspect. To help assess, the following guidelines are used: **Associated** – Event temporally related to the administration of the study product and no other etiology explains the event; and **Not Associated** – Event temporally independent of study product and/or the event appears to be explained by another etiology.

Serious Adverse Event (SAE)

An SAE is defined as an AE that meets one of the following conditions: (1) Death during the period of protocol defined surveillance; (2) Life threatening event (defined as a subject at immediate risk of death at the time of the event); (3) An event requiring inpatient hospitalization or prolongation of existing hospitalization during the period of protocol defined surveillance, results in congenital anomaly or birth defect, results in a persistent or significant disability/incapacity; or (4) Any other important medical event that may not result in death, be life threatening, or require hospitalization, may be considered a serious adverse experience when, based upon appropriate medical judgment, the event may jeopardize the subject and may require medical or surgical intervention to prevent one of the outcomes listed above.

All SAEs will be recorded on the appropriate SAE case report form, followed through resolution by a study clinician, and reviewed and evaluated by a study clinician.

Reporting Procedures for Serious Adverse Events

Any AE considered serious by the principal investigator or co-investigators or which meets the aforementioned criteria must be submitted on the SAE form to the IRB in accordance with IRB policies and procedures.

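### As written, any adverse event opens the treatment code, with no limit on the trigger, no named recipient and no rule that grading comes first

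*Combined protocol and SAP*

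**What the plan says.** Section 4.0 describes envelopes, taped syringes and clinic staff who do not disclose the arm, and concludes: "This will maintain the blinding for both the patient and research surgeons". On the master list it says: "The statistician will unlock the master list only after patient enrollment and follow-up are complete, or if mandated by any regulatory body". The next sentence adds a further case: "Blinding will also be uncovered in case of a patient developing an adverse event while being followed in the trial". Section 6.0, under dosage, preparation and administration, repeats the same pair of rules.

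Section 7.0 returns to the subject. It requires that "All AEs must be graded for severity and relationship to study product", and continues: "In such cases, the statistician will uncovering the patient blinding and randomization process to reveal the medication that was administered to the patient".

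The same section sets what counts as an AE:

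- The general definition is "any untoward medical occurrence in a patient or clinical investigation subject administered a pharmaceutical product regardless of its causal relationship".
- On a condition already present at screening: "However, if it deteriorates at any time during the study, it should be recorded as an AE".
- On uncertain observations, under relationship to study products: "If there is any doubt as to whether a clinical observation is an AE, the event should be reported".

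Section 9.0 calls the trial double-blinded and makes the 12-week ASES self-assessment score the main outcome. Section 5.0 has a blinded member of the research staff obtain the ASES by call or email. Section 6.0, under subject compliance, has the investigator who gives the injection also follow the patient to week 12.

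**The concern.** A code break in a double-blind trial is normally an exception with a stated reason and a short list of people who are told. Here an AE of any kind is enough, and the rule says that blinding *will* be uncovered, not that it may be.

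Two things are at stake. The main outcome is the patient's own rating of pain and function, so a patient who learned the drug before week 12 could score differently. The relationship of an AE to the product is a two-way clinician judgement (associated or not associated), and a clinician who knew the drug before making it could be influenced. For serious events, that judgement helps decide whether the report to the FDA is expedited or goes into an annual summary (Section 7.0, reporting procedures).

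**Working it through.** The point is procedural, so the check is mainly a comparison of passages. The plan's sample size is not in dispute and reproduces: 4 × (1.64 + 0.84)² × 12.3² / 12² = 25.85, rounded up to 26, and 26 / 0.8 = 32.5, rounded up to 33. Nothing below changes it.

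**1. Trigger.** Sections 4.0 and 6.0 name an AE during follow-up, with no qualifier. In Section 7.0, *in such cases* follows a sentence about all AEs. An earlier paragraph of that section deals expressly with events that are not serious, so the rule cannot be read as confined to serious ones.

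**2. Breadth.** The definition disregards cause, a worsening baseline condition counts, and doubtful observations are to be reported. A mild event with an obvious other cause therefore meets the trigger.

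**3. Recipient.** Section 7.0 names who opens the code (the statistician). No section names who is then told.

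**4. Order.** Section 7.0 mentions grading and then the reveal, but does not say that the grade must be recorded first. No other section does.

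**5. Who could be affected.** Severity is assessed by the clinician (Section 7.0). The injecting investigator also follows the patient (Section 6.0), so the grader may be the surgeon whom Section 4.0 sets out to keep blinded. Section 5.0 requires a blinded ASES collector but does not say that this person stays blinded after an AE.

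**6. Number of breaks, for scale only.** The protocol gives no AE rate. If a share p of the 40 planned patients has at least one AE, independently of each other, the expected number of codes opened is 40p, and the chance of at least one is 1 − (1 − p)^40.

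| Assumed p | Expected codes opened | Chance of at least one |
|---|---|---|
| 5% | 2 | 87% |
| 10% | 4 | 98.5% |
| 20% | 8 | over 99.9% |
| 30% | 12 | over 99.9% |

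**7. Effect on the score.** If patients were told, the bias in the ketorolac-minus-steroid difference would be p_K × s_K − p_S × s_S. Here p is the share told in each arm and s is the shift in ASES from knowing that drug. The protocol gives none of the four. As an illustration with assumed values, take 20% told in each arm. Equal shifts in the same direction cancel to 0. Opposite shifts of 6 points give 0.2 × 6 − 0.2 × (−6) = 2.4 points. Equal AE rates would therefore not guarantee an unbiased comparison, and no useful bound follows from the documents.

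**The case against.** **The passages do not flatly contradict each other.** The AE sentence in Sections 4.0 and 6.0 contains the word *also*, which marks it as one more listed exception to the master-list rule. The statement in Section 4.0 that blinding is maintained refers to preparing and giving the injection. A double-blind design is compatible with a code-break provision. All of this stands. What remains is an exception without limits.

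**The patient may never be told.** A reader might infer that patients learn their drug and that the main outcome is biased as a result. The documents do not support that. Section 7.0 speaks of revealing the medication given to the patient, not of revealing it to the patient. Section 4.0 says that the statistician and research coordinators have no patient contact, and Section 5.0 asks for blinded ASES collection. This stands, and it limits the point to a risk that the plan leaves open.

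**Grading first is a natural reading of Section 7.0.** That is fair, but the section does not require it, and a reveal attached to the grading requirement can equally be read as informing the grade. Section 7.0 also ties relatedness to timing and other causes, which limits the influence of knowing the drug without removing it.

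**Some unblinding is needed.** The stopping rule in Section 8.0 counts similar serious events within one therapy, and Section 7.0 requires regulatory reporting. Both are legitimate, but neither requires the patient, the grader or the ASES collector to know the assignment.

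**Conclusion.** The concern stands as a stated rule that, followed literally, opens the code early for any AE, in a trial described as double-blinded with a self-reported main outcome. It also stands that the recipient, the order of grading and reveal, and continued blinding after an AE are unspecified. These conclusions rest on the text alone and do not depend on any assumed rate.

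The documents do not show that breaks would be common, that they would differ by arm, or that ASES scores would move. A reader might want a figure for inflated type I error or lost power. Any such figure would come entirely from assumed shares and shifts, so none is offered. The counts of 2 to 12 opened codes rest on assumed AE rates of 5% to 30% and describe how often the rule would operate, not how much harm it would do. The rule should be fixed because the wording is clear and the remedy is cheap. Its effect on the result is unquantified.

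**What to change.** Reconcile Sections 4.0, 6.0 and 7.0 into one code-break rule consistent with the double-blind design in Section 9.0:

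- The trial team states the circumstances in which the code may be opened. Which clinical circumstances justify a break is for them to decide.
- Name the recipients and limit them to those who need to know. Withhold the assignment from the ASES collector and, where possible, from the patient and the clinician grading the AE.
- Record severity and relatedness before any reveal, unless urgent care prevents it.
- Log each break with date, reason and who was told, and report breaks by arm.
- Let the statistician, who has no patient contact, supply event counts by arm for the reporting in Section 7.0 and the stopping rule in Section 8.0.

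The cost is wording in three sections and a short log, using staff already planned. The downside is that relatedness will usually be graded without knowing the drug.

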
5.0 Study Procedures

Shoulder impingement is a syndrome characterized by shoulder pain that is exacerbated by passive and/or active elevation, with positive provocative testing for impingement such as Neer and Hawkins tests, and/or the diagnosis of subacromial bursitis based on tenderness to palpation of the acromion. Generally, patients who present with shoulder impingement will be treated initially with non-invasive measures such as activity modification, ice, physical therapy, and a trial of oral NSAIDs. If those measures do not provide adequate relief, then patients will be offered a therapeutic subacromial injection. The investigators will follow these principles of conservative management except when the patients' pain is

severely limiting their activities of daily living and their ability to work and provide for themselves or when patients are having pain at night that interferes with sleep. In those situations, a subacromial injection may be offered prior to attempting less invasive measures. Ultimately, the decision to offer a subacromial injection will be made in clinic by the investigators based on their clinical judgment. All of the investigators are fellowship-trained orthopedic surgeons who subspecialize in shoulder diseases. Their decision to offer patients a subacromial injection will be independent of whether the patients wish to participate in the study. Patients will be given the opportunity to participate in the study only after the decision to offer an injection is made by the clinician. Patients will not be solicited outside of a regularly scheduled clinic visit to participate in this study.

Investigational Drug Service (IDS) staff will not be directly involved with the handling of the study drugs; however, a plan has been documented and agreed upon by both parties regarding study drug supply, storage, randomization, preparation, administration, and accountability (Study Drug Management Form). Therefore, the clinic staff will maintain the blinding of the surgeons, who are licensed by the medical board of Texas to perform the injection.

[figure not shown]
[figure not shown]

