In addition, SAE's should be de-identified and anonymously reported to all investigators to emphasize on the possibility of other patients exhibiting a similar problem. The investigators are responsible of transmitting this information to their respective IRBs, who will then report the events that are serious, unexpected, and associated with the study product(s) to the Food and Drug Administration (FDA) within the required timelines as specified in 21 CFR Part 312.32: fatal and life-threatening events within 7 calendar days (by phone or fax) and all other SAEs in writing within 15 calendar days. All serious events designed as "not associated" to study product(s), will be reported to the FDA at least annually in a summary format.

The study clinician will complete a sponsor provided Serious Adverse Event Form within the following timelines: (1) All deaths and immediately life-threatening events, whether Protocol – Version 2 – November 13, 2018

related or unrelated, will be recorded on the Serious Adverse Event Form and sent by fax within 24 hours of site awareness; and (2) Serious adverse events other than death and immediately life-threatening events, regardless of relationship, will be reported via fax by the site within 72 hours of becoming aware of the event.

All SAEs will be followed until satisfactory resolution or until the principal investigator or co-investigator deems the event to be chronic or the patient to be stable.

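### The two relatedness classes leave no place for a contributing product, so a serious, unexpected event with a competing cause can reach the FDA in an annual summary instead of within 7 or 15 days

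*Combined protocol and SAP*

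**What the plan says.** Section 7.0, under Relationship to Study Products, sets a two-level scale: "All AEs must have their relationship to study product assessed using the terms: associated or not associated". Associated means: "Event temporally related to the administration of the study product and no other etiology explains the event". Not Associated means: "Event temporally independent of study product and/or the event appears to be explained by another etiology". The sentence that leads into these guidelines states: "In a clinical trial, the study product must always be suspect". The same paragraph says of the clinician's relatedness judgement that "it is not a factor in determining what is or is not reported in the study".

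Under Reporting Procedures for Serious Adverse Events, an event goes quickly to the FDA only if it is serious, unexpected and associated. The limit is 7 calendar days if it is fatal or life-threatening and 15 otherwise. For the rest: "All serious events designed as 'not associated' to study product(s), will be reported to the FDA at least annually in a summary format".

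Two other places use the label:
- Section 8.0, Termination of Study: when five similar serious events on one therapy halt recruitment, the FDA is told if the events are unexpected and judged associated with the drug.
- Section 6.0, Risks: the IRB hears only of serious, unanticipated problems associated with the injected product. Section 7.0 instead sends every serious adverse event to the IRB.

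**The concern.** The usual difficulty in judging relatedness is an event that follows treatment but also has another plausible cause. A two-level scale can handle it if the positive class includes a possible contribution from the product. Here the positive class requires that nothing else explains the event, and the negative class is met as soon as something else appears to. The doubtful case therefore goes to Not Associated, which is the reverse of treating the product as suspect.

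The label has consequences beyond description, because it chooses between the fast FDA route and the annual one. At stake is the timing of a safety report on an event that the sponsor did not anticipate and that the injection may have helped to cause.

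**Working it through.** No sample size, power or event rate enters this point. The check applies the definitions and reporting rules to each combination of facts.

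**Step 1. Relatedness class (Section 7.0 definitions).**

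| Follows the injection in time | Another apparent cause | Class |
|---|---|---|
| Yes | No | Associated |
| Yes | Yes | Not Associated |
| No | No | Not Associated |
| No | Yes | Not Associated |

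One of the four combinations is Associated. The second row is the problem: a product that may have contributed has no class of its own and falls on the negative side.

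**Step 2. FDA route for a serious event (Section 7.0 reporting procedures).**

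| Expectedness | Class | FDA route |
|---|---|---|
| Unexpected | Associated | 7 or 15 calendar days |
| Unexpected | Not Associated | At least annual summary |
| Expected | Associated | None stated |
| Expected | Not Associated | At least annual summary |

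**Step 3. Combine the two.** The definitions cost a fast report only when an event is serious, unexpected, temporally related and has a competing cause. If a full year separates summaries, the report can come up to 365 − 7 = 358 or 365 − 15 = 350 days later than the fast route allows. That is an upper limit, not an expected delay. Each patient is followed for 12 weeks (84 days), so the report can arrive after that patient has finished.

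**Step 4. Do the documents contain a case that fits?** Yes. Section 6.0, Risks, lists tendon rupture and infection as local effects of the steroid, but for ketorolac it lists systemic effects only. A serious local tendon event after subacromial ketorolac is therefore unlisted. Section 1.0 attributes the condition itself partly to supraspinatus tendonitis, which supplies a ready alternative explanation. Section 1.0 also gives a milder local tissue reaction as a possible advantage of ketorolac, so this signal bears on the trial's rationale.

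A gastrointestinal bleed is a weaker example. Section 5.0 says that patients are generally "treated initially with non-invasive measures such as activity modification, ice, physical therapy, and a trial of oral NSAIDs", which may offer another cause, but bleeding is already listed for ketorolac and so may count as expected. The documents name no reference for that judgement. Section 6.0 also argues that local delivery reduces systemic effects, so either answer could be defended.

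**Step 5. Safety stop (Section 8.0).** The trigger is five consistent serious events on one therapy, which is 5/20 = 25% of a planned arm. It carries no relatedness condition, but the FDA notice attached to it does. Five similar events, each with an apparent other cause, could halt recruitment without that notice. They would still appear in the annual summary.

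**Step 6. What does not depend on the label.** Adverse events are documented whatever their relationship. Serious-event forms are due in 24 hours for deaths and immediate threats to life and in 72 hours otherwise, related or not. Serious events are circulated to all investigators and, under Section 7.0, submitted to the IRB. If the Section 6.0 sentence on the IRB governs instead, relatedness limits IRB reporting as well.

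**The case against.** The strongest case on the other side has four parts.

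- **Named toxicities.** A reader might infer that the harms listed in Section 6.0 (tendon rupture after steroid; gastrointestinal bleeding, renal failure and myocardial infarction after ketorolac) drop out of fast FDA reporting. The documents do not support this. That route also requires the event to be unexpected. On a plain reading a listed effect is expected, so it never qualifies, whatever its relatedness class. This objection stands.
- **Biased safety results.** A reader might also infer that the count of related events is biased towards zero and that the safety conclusion rests on it. Section 9.0 plans analyses of the ASES score only and no analysis of related events. All events are recorded, so comparison of all events by arm remains possible. This objection also stands.
- **Guidelines applied by clinicians.** The definitions are offered as help to trained assessors who are told to suspect the product, and a mere risk factor is not an explanation. Section 3.0 excludes patients with gastrointestinal ulcers, bleeding disorders, kidney disease and full-thickness cuff tears, which removes several competing causes. The oral NSAID trial precedes the injection and is not said to continue. This limits how often the problem will arise. It does not change what the wording directs once another cause does appear to explain the event.
- **Other safeguards.** Most reporting ignores relatedness, as set out above. That stands, and it confines the effect to the FDA route, unless the Section 6.0 limit on IRB reporting is the one followed.

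**Conclusion.** The concern holds in a narrow form. The definitions class an event that follows the injection as Not Associated whenever another cause appears to explain it, against the paragraph's own principle. For serious, unexpected events of this kind, the FDA report moves from 7 or 15 days to an annual summary, and the FDA notice tied to a safety stop can be lost. The statement that relatedness does not determine what is reported is hard to square with a label that sets the FDA route and timing.

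The share of events affected is not given. It is probably small: an event must meet four conditions together, in 40 patients given one injection and followed for 12 weeks. The conclusion rests on reading and/or literally, and its reach depends on how unexpected is judged, which the documents leave open. No efficacy result is touched. This is a cheap improvement.

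**What to change.** In Section 7.0, redefine the two terms:

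- *Associated*: the event is temporally related and there is a reasonable possibility that the product or the injection contributed, even if another cause is present.
- *Not Associated*: the event is temporally independent; or another cause fully explains it and a contribution from the product is judged not reasonably possible, with the reason recorded.

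The FDA rules in Sections 7.0 and 8.0 can stay keyed to these terms. Three pieces of text should be settled at the same time:

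1. Reconcile Section 6.0, Risks, with Section 7.0 on which serious events go to the IRB.
2. State the reference against which an event is judged unexpected, for each drug by this route.
3. State the FDA route for serious events that are expected and associated. None is given now, and the new definition would move some expected events there from the annual summary.

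The cost is two sentences, the matching field on the adverse event form and these clarifications. The downside is that a few more events will be labelled associated and reported quickly. The redefinition does not bring expected toxicities into the 7- or 15-day route and should not be presented as doing so.
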